6.5 Quality of Life Measurement

The validated EORTC core quality of life questionnaire (QLQ-C30, version 3.0) supplemented by a brain cancer specific health-related quality of life questionnaire, QLQ-BN20, will be administered according to trial calendar. (Appendix V)

6.6 Define Progression

The progression of the glioma will be defined according to Updated Response Assessment

7.0 STATISTICAL PLAN

7.1 Sample Size Determination

We use 3+3 design for this trial. We estimate up to 24 patients.

7.2 Statistical Methods

We will use a two-stage accrual design at each dose considered. We will initially enter 3 subjects at each dose. If none of the three experiences a dose-limiting toxicity we will proceed to the next dose. If one of the three experiences that level of toxicity, we will accrue 3 more subjects at that dose. If at any time there are two or more dose-limiting toxicities (in the 3-6 subjects) on a given dose, we will terminate accrual to the Phase I portion of that trial. No patient will be treated at a higher dose until the 3 or 6 patients have completed their toxicity evaluation period at the current dose. With this plan, a dose with a 50% or greater probability of causing a dose-limiting toxicity has at most a 12.5% chance of satisfying the conditions for dose escalation after the first 3 subjects and at least a 50% chance of stopping at 3. With the two-stages (3-6) together, there is at most a 17.2% chance of satisfying the conditions for dose escalation after the 6 subjects.

The maximally tolerated dose (MTD) will then be the last dose studied or the previous dose, based on Investigator's clinical judgment of the degree of toxicity seen at the last dose. While waiting for the 3 or 6 subjects accrued according to plan to complete their toxicity evaluation period, up to 3 additional subjects may be accrued at the current dose. These additional subjects will not count towards the formal plan of stopping at two or more toxicity occurrences, but will contribute to the judgment as to the MTD.

We will also conduct some descriptive analyses that will help in the design of a possible phase-II trial. Among patients at the MTD in each arm, we will estimate the proportion with complete or partial response, as well as the median survival (through the Kaplan-Meier method). We will also compute associated 95% confidence intervals, although we realize that they will be very wide (given that we only anticipate 6-8 patients to be treated at the MTD in each arm). The estimates themselves, however, will help in the sample size calculations of possible future phase-II trials.

Progression free survival and overall survival will be measured from the date of starting study treatment (first day of radiation treatment). Progression free survival will be assessed by the treating physician based on the brain MRI.

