--	---

Study Therapy, Dose, Route, Regimen	Alisertib (MLN8237) will be administered by mouth, twice daily. The dose of Alisertib will be defined by the protocol.
Duration of administration and follow-up	Concurrent with radiation treatment, then 30 days after finishing radiation therapy will receive twice daily from day 1-7, every 21 day cycle for up to 18 cycles, or until tumor progression.
Reference therapy	None. This is a phase I study
Statistical Methodology	We will use a two-stage accrual design at each dose considered. We will initially enter 3 subjects at each dose. If none of the three experiences a dose-limiting toxicity we will proceed to the next dose. If one of the three experiences toxicity at that level, we will accrue 3 more subjects at that dose. If at any time there are two or more dose-limiting toxicities (in the 3-6 subjects) on a given dose, we will terminate accrual to the Phase I portion of that trial. No patient will be treated at a higher dose until the 3 or 6 patients have completed their toxicity evaluation period at the current dose. With this plan, a dose with a 50% or greater probability of causing a dose-limiting toxicity has at most a 12.5% chance of satisfying the conditions for dose escalation after the first 3 subjects and at least a 50% chance of stopping at 3. With the two-stages (3-6) together, there is at most a 17.2% chance of escalation.

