6.3 Dose escalation/de-escalation

Dose escalation will proceed within each cohort according to a “3+3 design”, as explained in the following scheme. Dose-limiting toxicity (DLT) is defined above. The toxicity assessment period is 30 days after the completion of the radiation therapy.

Dose Level	Alisertib dose
-1	10 mg BID
1	20 mg BID
2	30 mg BID
3	40 mg BID
4	50 mg BID (final dose level)

Number of Patients with DLT at a Given Dose Level[†]	Escalation Decision Rule
0 out of 3	Enter 3 patients at the next dose level.
≥ 2	Dose escalation will be stopped. This dose level will be declared the maximally administered dose (highest dose administered). Three (3) additional patients will be entered at the next lowest dose level if only 3 patients were treated previously at that dose.
1 out of 3	Enter at least 3 more patients at this dose level. 
 • If 0 of these 3 patients experience DLT, proceed to the next dose level.

	
 If 1 or more of this group suffer DLT, then dose escalation is stopped, and this dose is declared the maximally administered dose. Three (3) additional patients will be entered at the next lowest dose level if only 3 patients were treated previously at that dose.
≤1 out of 6 at highest dose level below the maximally administered dose	This is generally the recommended phase 2 dose. At least 6 patients must be entered at the recommended phase 2 dose.
†Dose escalation will be determined based on the occurrence of DLTs. For the purposes of determining whether to advance the Dose Level, DLTs will be counted by patient (i.e., a patient who experiences more than 1 DLT will be counted only once).	

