8.4 Stopping Rules

Enrollment will stop if there are two or more DLTs in any one dose cohort and the MTD will be defined as the next lowest dose.

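### After two or more DLTs at a dose, sections 7.2, 8.4 and 6.3 give inconsistent instructions on the MTD and on further enrolment, and none takes precedence

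*Combined protocol and SAP*

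**What the plan says.** Three current sections say what happens when a dose meets the stopping rule.

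- **Section 7.2**, with the stop repeated in the Study Summary under Statistical Methodology: "If at any time there are two or more dose-limiting toxicities (in the 3-6 subjects) on a given dose, we will terminate accrual". The MTD "will then be the last dose studied or the previous dose", chosen on the investigator's view of the toxicity seen at the last dose. Up to three additional patients may be accrued at the current dose while the formal patients are still being evaluated. These "will not count towards the formal plan of stopping at two or more toxicity occurrences, but will contribute to the judgment" as to the MTD.
- **Section 8.4**: enrolment stops after "two or more DLTs in any one dose cohort and the MTD will be defined as the next lowest dose". It allows no judgment and sets no minimum number treated at that lower dose.
- **Section 6.3**: escalation stops, and "Three (3) additional patients will be entered at the next lowest dose level if only 3 patients were treated previously" at that dose. A dose with at most 1 DLT in 6 "at highest dose level below the maximally administered dose" is generally the recommended phase 2 dose, and "At least 6 patients must be entered at the recommended phase 2 dose". Section 6.3 does not mention the MTD. Its dose table includes 10 mg BID as level -1, below the 20 mg BID starting dose.

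Section 1.1.1 lists the MTD and the recommended phase 2 dose as two outputs and does not say how they relate. I found no statement of which section governs.

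**The concern.** Determining the MTD is a primary objective (section 2.1) and a primary endpoint (section 3.2). The rule that turns DLT counts into an MTD should therefore give one answer for one set of data, and here it does not. There are two separate faults.

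1. Section 7.2 permits the investigator to name the dose that has just met the stopping rule. Section 8.4 does not.
2. Sections 7.2 and 8.4 both stop enrolment at the point where 6.3 may require more of it.

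The stakes are a failed dose reported as the MTD, or an MTD declared without the further patients that 6.3 asks for.

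**Working it through.** **Step 1. Reproduce the plan's figures.** Section 7.2 gives 12.5%, 50% and 17.2% for a dose with a true DLT rate p of 50%.

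- Escalate after 3: (1-p)^3 = 0.125.
- Stop at 3: P(2 or more of 3) = 3(0.5)^2(0.5) + (0.5)^3 = 0.500.
- Escalate over both stages: (1-p)^3 + 3p(1-p)^2 × (1-p)^3 = 0.125 + 0.375 × 0.125 = 0.1719.

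All three are correct. They limit the chance of escalating past such a dose. They say nothing about the chance that 7.2 lets the same dose be named MTD after it fails.

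**Step 2. Apply each section to the same data.**

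| Data | 7.2 | 8.4 | 6.3 |
|---|---|---|---|
| 0/3 at 20 mg, 2/3 at 30 mg | Accrual ends; MTD 20 or 30 mg | Enrolment ends; MTD 20 mg | Three more at 20 mg first |
| 1/6 at 20 mg, 2/3 at 30 mg | Accrual ends; MTD 20 or 30 mg | Enrolment ends; MTD 20 mg | No one added; 20 mg generally the recommended phase 2 dose |
| 2/3 at 20 mg | Accrual ends; 20 mg permitted | Enrolment ends; MTD 10 mg, given to no one | Dose table provides 10 mg as level -1 |

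In the first row both faults appear. In the second only the choice of MTD is in conflict, because the lower dose already has six patients. In the third, 8.4 names a dose while stopping the enrolment needed to test it.

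A fourth case is 50 mg reached without failing. Taking the last dose studied is the natural reading of 7.2, but 8.4 is silent, and the 6.3 row on the recommended dose covers only levels below a failed one.

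**Step 3. How often would the lower dose have passed on only three patients?** The documents give no DLT rates for this combination, so the rates are assumed. The calculation also assumes that none of 7.2's extra patients were accrued at that dose. A dose passes on 0/3 or on 1/3 followed by 0/3, so P(pass) = (1-p)^3 + 3p(1-p)^5, and the share passing on 0/3 is (1-p)^3 / P(pass).

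| p | (1-p)^3 | P(pass) | Share on 0/3 |
|---|---|---|---|
| 0.10 | 0.7290 | 0.9061 | 80% |
| 0.20 | 0.5120 | 0.7086 | 72% |
| 0.33 | 0.3008 | 0.4344 | 69% |

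**Step 4. What 0/3 supports.** The one-sided 95% exact upper limit for the DLT rate after 0/3 is 1 - 0.05^(1/3) = 0.632, or 63%.

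**Step 5. What 6.3's three further patients could change.** After 0/3, two or more DLTs among the next three take the dose above 1 in 6. The probability is 3p^2(1-p) + p^3 = 0.104, 0.255 and 0.500 at p = 0.20, 0.33 and 0.50. In those cases the dose already named by 8.4 would not meet 6.3's criterion.

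**The case against.** The strongest reply is that this is a familiar 3+3 and that stopping accrual means stopping escalation. Read that way, the enrolment conflict goes away. The MTD conflict remains, because 7.2 expressly offers the last dose studied and 8.4 excludes it. The medical monitor's review before escalation (section 10.1) does not define the MTD either.

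Other points limit how far the criticism can go.

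- A reader might infer that 7.2 and 8.4 can never both be obeyed. They can: naming the previous dose satisfies both. The fault is that 7.2 also permits a failed dose.
- A reader might infer that the dose taken into phase 2 could rest on three patients. Section 6.3's minimum of six rules that out for the recommended phase 2 dose. The minimum does not clearly reach the MTD under 8.4, because no text links the two.
- A reader might infer that stopping always contradicts 7.2's own statement that "we only anticipate 6-8 patients to be treated at the MTD in each arm", or that 8.4 always leaves an MTD tested in three. Neither follows. Three formal patients plus up to three extras can make six with no enrolment after the stop, and could also mean that 6.3's condition of only three treated is not met.
- Keeping the extras out of formal stopping is a disclosed design choice, not an error. What is missing is a statement in 6.3 and 8.4 of whether the exclusion applies there too.

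**Conclusion.** The rules are wrong as written. The same DLT data can give different MTDs depending on the section followed, and two sections stop enrolment that a third may require. This conclusion rests on the wording alone and needs no assumed rate.

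The size of the enrolment conflict does depend on assumptions. With true rates of 10, 20 and 33% at the lower dose and no extras accrued there, 80, 72 and 69% of passing doses would have passed on 0/3. The three further patients would then overturn the dose with probability 10, 25 and 50% at true rates of 20, 33 and 50%.

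The stated 17.2% stands as a limit on escalation. A reader might take its complement, 100 - 17.2 = 82.8%, as the chance that a dose with a 50% DLT rate is wrongly named MTD. The documents do not support that. It is the chance that such a dose, if tested, meets the stopping rule, after which 7.2 permits it to be named. What the investigator would then choose is unknown.

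**What to change.** - Make the 6.3 table the single decision rule. Have the Study Summary, 7.2 and 8.4 refer to it and not restate it.
- Define the MTD as the highest dose with at most 1 DLT in 6 formally evaluated patients, and state whether the recommended phase 2 dose is the same dose.
- Remove the option in 7.2 to name a dose that met the stopping rule. Judgment may only select a lower dose.
- State that enrolment continues after a failure as 6.3 requires, including at 10 mg BID if 20 mg fails. This needs its own sentence, because 6.3's instruction is worded for a level where three patients were already treated.
- State that 50 mg is completed to six patients before it is named.
- State in 6.3 and 8.4 whether 7.2's extra patients count toward stopping.

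The cost is wording, plus up to three patients at the chosen dose, which 6.3 already requires. Four levels of six make 24, which matches the planned maximum. Rare paths that step down to level -1 can exceed it. For example, if 50 mg fails on its first three patients and 40, 30 and 20 mg are each filled to six and fail, six patients at 10 mg give 3 + 6 + 6 + 6 + 6 = 27. The sample size statement should allow for this.

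### Section 7.2 leaves additional patients' DLTs out of the two-or-more count, so its formal rule can permit escalation where 6.3, and on its plain wording 8.4, would stop

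*Combined protocol and SAP*

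**What the plan says.** Three sections of the combined protocol and SAP govern the same decision.

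- **7.2 Statistical Methods** applies the stop to the planned patients: "If at any time there are two or more dose-limiting toxicities (in the 3-6 subjects) on a given dose". While they are being evaluated, "up to 3 additional subjects may be accrued at the current dose". Of these it says: "These additional subjects will not count towards the formal plan of stopping at two or more toxicity occurrences". They inform the clinical judgement of the MTD. The hold on escalation is also tied to the planned patients: "No patient will be treated at a higher dose until the 3 or 6 patients have completed their toxicity evaluation period".
- **6.3 Dose escalation/de-escalation** tabulates the number of patients with DLT at a given dose level and ends escalation at two or more. That row has no denominator, and no class of patient is left out. The footnote says only that "DLTs will be counted by patient (i.e., a patient who experiences more than 1 DLT will be counted only once".
- **8.4 Stopping Rules** reads: "Enrollment will stop if there are two or more DLTs in any one dose cohort". It does not mention additional patients.

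For a dose with a DLT probability of 50% or more, 7.2 states that it "has at most a 12.5% chance of satisfying the conditions for dose escalation after the first 3 subjects". It puts the probability of a stop after three patients at 50% or higher, and the probability of escalating over both stages at no more than 17.2%.

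**The concern.** Suppose none of the three planned patients has a DLT but two of three additional patients do. Under 7.2 the formal condition for escalation is met. Under the wording of 6.3, two patients at that dose level have had a DLT and escalation stops. Under the plain wording of 8.4, enrollment stops. Two careful readers of the same protocol, with the same data, can reach opposite decisions.

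Timing adds a second gap. Because the hold in 7.2 covers only the planned 3 or 6, additional patients enrolled later may still be in their 30-day post-radiation window when the next level opens.

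At stake are exposure of new patients to a higher dose and the MTD, which is a primary objective.

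**Working it through.** **Inputs.** From 7.2: three patients, then three more if one of the first three has a DLT; stop at two or more DLTs in the planned patients; up to three additional patients, whose DLTs are not counted; benchmark DLT rate p = 0.5.

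**Assumptions (mine).** Outcomes are independent with a common DLT rate p. The m additional patients (m = 1, 2 or 3 in total at a dose) have known results when the decision is taken. Except where stated, they are separate from the second-stage three.

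**Step 1: reproduce the plan's figures at p = 0.5.**
- P(0 of 3) = 0.5³ = 0.125, the stated 12.5%.
- P(2 or more of 3) = 0.375 + 0.125 = 0.50, the stated 50%.
- P(escalate) = P(0 of 3) + P(1 of 3) × P(0 of 3) = 0.125 + 0.375 × 0.125 = 0.125 + 0.046875 = 0.171875, the stated 17.2%.

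All three are correct for the planned 3 to 6 patients.

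**Step 2: which outcomes the 7.2 rule lets through.**
- 0 of 3 planned plus 2 or 3 additional patients with DLT: 2 or 3 DLTs in 5 to 6 treated.
- 1 of 6 planned plus 1 to 3 additional patients with DLT: 2 to 4 DLTs in 7 to 9 treated.

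**Step 3: how often.** With X the number of DLTs among the m additional patients, X ~ Bin(m, p):

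P(formal escalation and at least 2 DLTs at the dose) = P(0 of 3) × P(X ≥ 2) + P(1 of 3) × P(0 of 3) × P(X ≥ 1).

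Subtracting this from 0.171875 gives the escalation probability if every DLT at the dose counted. At p = 0.5:

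| m | Escalation with ≥2 DLTs seen | Escalation if all DLTs counted |
|---|---|---|
| 1 | 0.046875 × 0.5 = 0.02344 (2.3%) | 0.14844 (14.8%) |
| 2 | 0.125 × 0.25 + 0.046875 × 0.75 = 0.06641 (6.6%) | 0.10547 (10.5%) |
| 3 | 0.125 × 0.5 + 0.046875 × 0.875 = 0.10352 (10.4%) | 0.06836 (6.8%) |

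**Step 4: alternative reading.** Section 7.2 does not say whether additional patients may become the second-stage three. If three of them do, and all DLTs count, escalation needs 0 of 3 followed by at most 1 of 3, or 1 of 3 followed by 0 of 3: 0.125 × 0.5 + 0.375 × 0.125 = 0.109375, or 10.9%.

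**Step 5: a lower DLT rate, p = 0.3, m = 3.**
- As written: 0.343 + 0.441 × 0.343 = 0.343 + 0.15126 = 0.49426 (49.4%).
- With at least 2 DLTs seen: 0.343 × 0.216 + 0.15126 × 0.657 = 0.07409 + 0.09938 = 0.17347.
- If all counted: 0.49426 − 0.17347 = 0.32079 (32.1%).

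**The case against.** The best defence is that 7.2 is deliberate and is the only text that deals with additional patients, so it should govern. The other rows of the 6.3 table use denominators of 3 and 6, which fits a plan about the planned patients. Its footnote concerns several DLTs in one patient, not which patients count. In 8.4, cohort is undefined and could mean only the planned 3 or 6. That softens the conflict with 8.4. It does less for 6.3, whose count is by dose level and whose stopping row carries no denominator. A deliberate rule in 7.2 would still need 6.3 to say the same.

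A reader might infer that DLTs in additional patients are simply ignored. The documents do not support that. Section 10.1 has the medical monitor review adverse events and safety data at each new dose level before escalation, with power to recommend suspension or termination, and 7.2 uses these patients in judging the MTD. Escalation under 7.2 is permitted, not compelled. But neither provision sets a numerical stop, and 7.2 links the additional patients to the MTD judgement, not to the escalation decision.

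A reader might also take the three-patient result as the general effect: 10.4 of 17.2 points, about 60% of escalations at a 50% DLT rate. That is the worst case. It needs all three additional patients enrolled and their results known, whereas they are accrued while the planned patients are under evaluation and may well finish later. Nor can escalation past a toxic dose arise at 50 mg BID, the final level.

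**Conclusion.** The inconsistency stands. Followed exactly, 7.2 can permit escalation on data for which 6.3 stops it and for which 8.4, unless cohort is read narrowly, stops enrollment. This is a single-center trial, so the risk is of different readings of one document, not of divergence between sites.

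At a 50% true DLT rate, between 2.3 and 10.4 percentage points of the 17.2% escalation probability, depending on whether one or three additional patients are treated, are escalations with two or more DLTs already seen at the dose. This rests on independent outcomes, a common DLT rate and known results. Where results are not yet known, the problem is instead that the next level may open before those DLTs can appear.

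It would be wrong to infer that the stated 12.5% and 17.2% are miscalculated: they are right for the planned 3 to 6 patients. The documents do not settle which count was intended, and no view is taken here on which escalation rule is right.

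**What to change.** Reconcile 6.3, 7.2 and 8.4 so that all three state the same rule on two points: which patients' DLTs count toward the two-or-more rule, and whose evaluation window must close before a higher dose opens. Define cohort in 8.4, and say in 7.2 whether additional patients may serve as the second-stage three. Restate the escalation probabilities for the rule adopted.

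The edit is short. Its operating cost depends on the sponsor's choice. If additional patients are counted, escalation becomes materially less likely, also at lower DLT rates: for example 32.1% instead of 49.4% at a 30% rate with three such patients. It may also have to wait for their windows to close. If they are not counted, escalation stays as 7.2 now has it, but 6.3 and 8.4 must state the exclusion openly.

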7.3 Subject Population(s) for Analysis

All subjects who received the radiation treatment per the protocol and concurrent Alisertib will be subjected to the study analysis – both for the primary analysis and any applicable secondary analyses.

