1.3 Study Therapy

1.3.1 FSRT

Fractionated stereotactic surgery (FSRT) will be administered once daily, every weekday for a total of 10 daily treatments. All subjects will receive the 30-35 Gy in 10 daily fractions, as determined by the treating physician. Radiation treatment interruptions for up to 3 days are permitted for any reason. Interruptions of 4 to 7 treatment days will be considered an acceptable protocol violation. For interruptions of 8 days or greater, an unacceptable deviation will be assigned.

All patients will have CT simulation and high resolution MRI with contrast for radiation treatment planning. The gross tumor volume (GTV) will be defined by the contrast-enhanced T1 abnormality on the post-operative MRI scan. This will generally include the surgical cavity margins from the most recent surgical procedure as well. There is no clinical target volume (CTV) or planned target volume (PTV) expansion.

All patients will receive 35 Gy in 3.5 Gy fractions. This dose may be reduced to 30 Gy in 10 fractions per the treating physician if the GTV is large (> 50 cc) or close to critical structures (such as brainstem, optic nerves, or chiasm). The dose is prescribed to the highest isodose line that covers >99% of the GTV.

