4.5.2 Data Collection and Follow-Up for Withdrawn Subjects

According to FDA regulations, when a subject withdraws from the study, the data collected on the subject to the point of withdrawal remains part of the study database and may not be removed.

A subject who discontinues study treatment needs to state whether he/she wishes to continue participating in the study and allow further data collection as part of long term follow-up. Subjects who choose to continue with the study will participate in follow-up visits and evaluations according to the protocol. Subjects who refuse to participate in follow-up will be withdrawn from the study.

Study data collected prior to a subject's withdrawal from the study will be included in the study analysis.

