5.2 Treatment Regimen

Alisertib will be administered by mouth, twice daily on days of radiation treatment during the course of FSRT. All patients will receive 10 days of Alisertib, concurrent with 10 daily radiation treatments. The first dose should be administered on the day of, but prior to, the first radiation treatment. The dose of Alisertib will be determined according to the protocol.

During the maintenance therapy period, Alisertib will be administered by mouth, at 50 mg twice daily from day 1 to day 7 of a 21-day cycle. All patients will receive up to 18 cycles, or until tumor progression

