6.2 Definition of Dose-Limiting Toxicities

Dose-limiting toxicities (DLTs) will be graded in severity according to the guidelines outlined in the NCI-CTCAE version 4.0. Dose-limiting hematologic and non-hematologic toxicities will be defined differently, and will be based on events that occur during study drug administration and for 30 days after the completion of the radiation therapy. In order to be declared a dose-limiting toxicity, an adverse experience must be related (definitely, probably, or possibly) to study therapy.

If a patient experiences a DLT during the radiation phase or the 30 day post radiation observation period, the patient will be permanently discontinued from study.

A dose-limiting toxicity (DLT) will be defined as follows:

- All grade 3 or higher toxicities that occur during or within 30 days of completing radiation treatment will be considered “treatment related” with the exception of (1) symptoms that are clearly related to the cancer or other pathology (in the opinion of the treating physician), and (2) expected sequelae of the neurosurgical procedure or radiosurgery. All neurological symptoms will be considered “treatment related” unless they are present at study onset, expected sequelae of the neurosurgical procedure, or clearly related to disease progression.
- Febrile neutropenia (even in the absence of hospitalization)
- Hematologic DLTs will be defined as either Grade 4 neutropenia lasting for ≥ 7 days in duration, any Grade 4 anemia, any Grade 4 thrombocytopenia, or any Grade 5 hematologic toxicity. All patients will be evaluated for hematologic toxicity.
- Any neurological toxicity of Grade 3, 4 or 5 will be considered a DLT, with the exception of 1) symptoms present prior to study enrollment, and 2) expected sequelae of the neurosurgical procedure.
- Grade 3 event of hypocalcemia, hypophosphatemia, hypokalemia, or hypomagnesemia lasting more than 24 hours without responding to medical therapy; or responding to medical therapy and lasting more than 72 hours
- Grade 3 transaminases elevation associated with \geq grade 2 bilirubin elevation (Hy’s law)

will also be a DLT defining event.

- Non-hematologic dose-limiting toxicity will be defined as any Grade 3, 4 or 5 non-hematologic toxicity, with the specific exception of:
 - Grade 3 nausea or Grade 3 vomiting that in the opinion of the Investigator occurs in the setting of inadequate compliance with supportive care measures and lasts for less than 48 hours.

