6.4 Dose Delay and Dose Modification

If a patient experiences DLT during the radiation phase or 30 day post radiation observation period the patient will be permanently discontinued from the study.

Maintenance treatment with Alisertib will be repeated every 21 days. In order for a new cycle of therapy to begin, the patient's ANC must be $\geq 1,500/\text{mm}^3$ and the platelet count must be $\geq 75,000/\text{mm}^3$. In addition, any other toxicity considered by the investigator to be related to therapy with Alisertib must have resolved to \leq Grade 1 or to the patient's baseline value before a new cycle of therapy may begin.

If the patient fails to meet the above-cited criteria for retreatment, then initiation of the next cycle of therapy will be delayed for up to 1 week. At the end of that week, the patient will be re-evaluated to determine whether the criteria for retreatment have been met. Should treatment need to be delayed for more than 1 week (i.e., a rest period of more than 21 days) because of incomplete recovery from treatment-related toxicity, the dose of Alisertib will be reduced 1 level when therapy resumes. A second dose reduction may occur should treatment need to be delayed for more than 1 week because of incomplete recovery from treatment-related toxicity on the reduced dosage. Should treatment need to be delayed for more than 2 weeks at any dose, therapy with Alisertib will be discontinued (Table 1).

Dose Level	Dose	Schedule
1	50 mg	PO BID
-1	40 mg	PO BID
-2	30 mg	PO BID
-3	Discontinue	
Level 1 is the standard maintenance dose of 50 mg BID.		

Dose Modifications for Hematological Toxicity

If a patient experiences any of the following hematological toxicities during the dosing period, dosing will be discontinued for the remainder of that cycle and the dose will be decreased 1 level for all subsequent cycles of treatment.

1. _____
2. Grade 4 thrombocytopenia (platelet count $< 25,000/\mu\text{L}$) lasting more than 7 consecutive

days

3. Grade 3 neutropenia with fever or infection, or both, where fever is defined as an oral temperature greater than 38.5°C
4. Grade 3 thrombocytopenia with clinically significant bleeding

If a patient has a platelet count of less than 10,000/ μ l at any time, the patient will be removed from the study permanently.

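### Section 7.3 ties every analysis to radiation received per protocol; read literally, it drops patients whose course was cut short, including by a DLT, and it is not reconciled with 4.5.2

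*Combined protocol and SAP*

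**What the plan says.** Section 7.3 reads "All subjects who received the radiation treatment per the protocol and concurrent Alisertib will be subjected to the study analysis", and its sentence goes on to cover both the primary analysis and any secondary ones. No separate safety or DLT-evaluable set is defined anywhere.

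The planned course is in 5.2: "All patients will receive 10 days of Alisertib, concurrent with 10 daily radiation treatments". Section 1.3.1 sorts radiation interruptions into three classes. Up to 3 days is permitted. Beyond that, "Interruptions of 4 to 7 treatment days will be considered an acceptable protocol violation", and "For interruptions of 8 days or greater, an unacceptable deviation will be assigned". It does not say which classes still count as radiation per protocol when the data are analysed.

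On toxicity, 6.2 says "If a patient experiences a DLT during the radiation phase or the 30 day post radiation observation period, the patient will be permanently discontinued", and 6.4 repeats the rule. On withdrawn subjects, 4.5.2 says "Study data collected prior to a subject's withdrawal from the study will be included in the study analysis".

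**The concern.** Safety and tolerability is the first primary objective. A DLT during the ten-fraction course takes the patient off study, so the course may be left unfinished. Such a patient has not received the radiation that 5.2 describes and, on a literal reading of 7.3, is not in the analysed population. The event the trial exists to measure could then remove the patient from the reported safety and DLT results. The patient would also leave the progression-free survival (PFS) and overall survival (OS) results, although 7.2 starts both clocks on the first day of radiation, a date that does not depend on finishing the course.

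The reported DLT rate could then disagree with the count that drove escalation. Because the per-protocol condition is undefined, the analyst would have to settle its meaning after seeing who failed to complete and why.

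**Working it through.** **The plan's own figures.** Section 7.2 states operating figures at a true DLT probability of p = 0.5. With exact binomial arithmetic:

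- Escalate after 3: (1 − p)³ = 0.5³ = 0.125, or 12.5%.
- Stop at 3 (two or more DLTs in three): 3p²(1 − p) + p³ = 0.375 + 0.125 = 0.500, or 50%.
- Escalate over both stages: (1 − p)³ + 3p(1 − p)² × (1 − p)³ = 0.125 + 0.375 × 0.125 = 0.171875, or 17.2%.

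All three reproduce. They rest on DLT counts among the 3 or 6 patients at a dose. Sections 6.3, 7.2 and 8.4 attach no condition that radiation was completed, so the wording of 7.3 does not change them.

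**Who is in the analysis, by type of patient.**

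| Patient | 7.3 read literally | 4.5.2 |
|---|---|---|
| DLT during radiation, course cut short | Out | Data up to withdrawal are in |
| DLT in the 30 days after a completed course | In | Data up to withdrawal are in |
| Withdrawn during radiation for another reason in 4.5.1 | Out | Data up to withdrawal are in |
| Stays on study, interruption of 4 days or more | Undefined | Not addressed |

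The passages diverge in the first and third rows. In the fourth, neither settles the matter.

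**Effect on the reported DLT rate.** Let N be the patients treated at a dose, D those with a DLT, and d the DLT patients dropped because radiation was cut short. The reported rate is (D − d)/(N − d). Take N = 6 and D = 1, the largest count 6.3 generally accepts at the recommended phase 2 dose.

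- d = 0: 1/6 = 16.7%. The exact (Clopper-Pearson) 95% interval is 0.4 to 64.1%.
- d = 1: 0/5 = 0%. The interval is 0 to 52.2%, the upper limit being 1 − 0.025^(1/5) = 0.522.

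The intervals only show the precision; the protocol plans none for the DLT rate. D = 1 and d = 1 are assumptions chosen for illustration. The documents do not say how many DLTs would fall within the radiation course or how many of those would cut it short.

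**The case against.** The best defence is that the two passages do not conflict. Both are statements of inclusion: 7.3 says certain subjects will be analysed, and 4.5.2 says withdrawn subjects' earlier data will be. Analysing everyone treated satisfies both. Section 7.3 does not limit the analysis to the subjects it names, 4.5.2 is the more specific rule for withdrawals, and stopping for a DLT is itself a protocol step. It can be added that adverse events are recorded and reviewed for everyone under sections 8 and 10, that escalation is untouched, and that several things must happen before harm occurs: the DLT must arise during radiation, the remaining fractions must be omitted (6.2 and 6.4 do not say so), and 7.3 must then be read restrictively.

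Much of this stands. It shows that exclusion is not certain and that the effect is confined to reporting. It does not remove the problem. A sentence that describes the analysed subjects by a condition is naturally read as defining the set, and it is the only definition in the plan. Recording and oversight do not determine who is in the reported numerator and denominator. Section 4.5.2 sets no denominator and does not cover a patient who stays on study after a long interruption.

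A reader might go further and infer that the plan excludes DLT patients outright, or that the maximum tolerated dose is biased and the chance of escalating past a toxic dose exceeds 17.2%. The documents support neither. The first ignores 4.5.2 and the benign reading of 7.3. The second would need 7.3 to govern the escalation count, whereas 6.3 counts DLTs by patient with no completion condition.

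**Conclusion.** The point holds as an unresolved ambiguity in the only stated analysis population, and one of its readings biases the primary safety result. On that reading, one excluded radiation-phase DLT among six treated patients turns a reported 16.7% into 0%. This assumes that the DLT occurs during radiation, that the course is then cut short, and that 7.3 is applied literally over 4.5.2. The first two have no stated frequency, so the figure shows what could happen to one cohort and is not an expected bias. The ambiguity should be settled before analysis, since settling it costs almost nothing.

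**What to change.** Amend 7.3 to state that:

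1. Safety and DLT reporting, PFS and OS include every subject who received any alisertib or any protocol radiation fraction.
2. No interruption or deviation class in 1.3.1 removes a subject from these analyses.
3. Section 4.5.2 governs the data of withdrawn subjects.
4. Subjects who did not complete radiation or the 30-day window are listed with the reason.
5. Any completers-only or DLT-evaluable summary is supplementary, keeps every treated patient with a DLT, and does not alter the 3 to 6 patient counts in 6.3 and 7.2.

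The cost is one paragraph. Reported rates may shift slightly in either direction compared with a literal reading of 7.3: keeping a DLT patient raises the rate, and keeping a DLT-free patient who did not complete lowers it. Sample size, escalation, treatment-stopping rules and the stated operating figures stay as they are.
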